5.2 Randomization/Treatment Assignment

All subjects will receive tapinarof cream, 1% QD for 27 days.

5.3 Blinding

This will be an open label study.

5.4 Compliance with Study Drug Administration

At Baseline, study staff will provide the subject and/or caregiver with detailed instructions concerning protocol requirements and use of study drug. Additionally, subjects and/or caregivers will be asked to complete a daily diary with the time of each application of study drug, except on study visit days. At each post-Baseline study visit, study staff will review use of study drug, as applicable, with the subject. Subject compliance will be assessed via study diary completion.

When subjects are dosed at the site, they and/or their caregivers will apply the study drug under supervision of the study staff. The date and time of each dose administered in the clinic will be recorded in the source documents. In clinic doses are not recorded in the subject's daily diary. The study drug and study subject identification should be confirmed at the time of dosing by a member of the study site staff other than the person dispensing the study drug.

At the time of dispensing study drug to each subject, site personnel will weigh the tubes to be dispensed with the cap on and will record the weight of all tubes dispensed at each visit in the drug accountability logs.

Subjects and/or caregivers will be instructed to bring all used and unused tubes with them to each study visit. Site personnel will weigh the returned tubes (used and unused) with the cap on and record the weight in the drug accountability logs. If a tube has been lost, discarded, or forgotten by the subject, then the site personnel will make a notation of this on the drug accountability logs. Forgotten tubes should be returned by the subject at the next study visit. Tubes of study medication dispensed at the most recent prior visit which remain unopened (the foil cap on the tube remains fully intact/undisturbed) may be re-dispensed to study subjects at the current visit. Unopened tubes may only be re-dispensed once. Opened, partially used tubes or tubes with

foil overlay removed are not to be re-dispensed to study subjects. If there is any question as to re-dispensation, sites should issue new tubes of study medication to the subject(s).

5.5 Treatment after the End of the Study

Subjects will not receive any additional treatment with the study drug from the Sponsor after completion of the study (with the exception of eligible subjects who enroll in the open-label, long-term safety study) because the indication being studied is not life threatening or seriously debilitating and other treatment options are available.

The Investigator is responsible for ensuring that consideration has been given to the poststudy care of the subject's medical condition, whether or not the Sponsor is providing specific poststudy drug.

5.6 Prior and Concomitant Therapy

Any medication (including over the counter or prescription medication, vitamins and/or herbal supplements) administered to the subject up to 30 days before the Screening visit, at the time of enrollment, and during the study must be recorded in the CRF along with the reason for use. The information to be recorded must also include name of the medication (generic name, as a general rule), dose, frequency, administration routes, and dates of the first and last dose, as applicable.

The Medical Monitor should be contacted if there are any questions regarding concomitant or prior therapy.

5.6.1 Permitted Medications and Nondrug Therapies

Concomitant medications for medical treatment of other conditions are allowed under the condition that the dosage and administration of these treatments is not planned to change from the Baseline visit to the completion of the treatment phase (Day 28) and that the medication is not a prohibited medication as described in the Exclusion Criteria (Section 4.3).

In the event of skin infection, topical antibacterial agents with the exception of gentamicin and neomycin sulfate can be applied to the infected area; however, study drug must not be applied to the area until the skin infection is healed.

Nonmedicated emollients that do not contain salicylic acid may be used on nonlesional skin; but the subject (or caregiver) should wait at least 30 minutes after applying study drug before applying nonmedicated emollients. Emollients should not be applied to lesional skin during treatment. The same emollient should be used throughout the subject's participation in the study.

NOTE: Any emollient used during the study must be recorded as a concomitant medication.

5.6.2 Prohibited Medications and Nondrug Therapies

Medications and nondrug therapies that are prohibited throughout the study duration are described in the Exclusion Criteria (Section 4.3). A list of prohibited medications, emollients and nondrug therapies may be provided as a separate document.

If a subject chooses to treat scalp with study drug, then medicated shampoos that contain coal tar, salicylic acid, or hydrocortisone are prohibited for use. Emollients containing salicylic acid are prohibited.

6 Study Assessments and Procedures

Study procedures and assessments are summarized in the Schedule of Assessments and in Section 6.

Adherence to the study design requirements, including those specified in the Schedule of Assessments (Table 1) are essential and required for study conduct. Protocol waivers or exemptions are not allowed, except for immediate safety concerns.

6.1 Demography, Medical History, and Baseline Characteristics

6.1.1 Demographics

Demographic information collected will include age, sex, race, ethnicity, and Fitzpatrick skin type.

Information on Fitzpatrick skin type can be found in [Appendix 2](#).

6.1.2 Medical History

Medical history will be collected to ensure subjects are eligible for participation in the study (per inclusion Section 4.2 and exclusion Section 4.3 criteria).

Data collected will include month and year of AD diagnosis, allergic conditions, and cardiovascular (CV) medical history risk factors (including height, weight, blood pressure, medical conditions, and family history of premature CV disease) and family history of liver disease.

As part of the subject's disease history, all systemic (oral and injectable) medications used by the subject for treatment of AD prior to 30 days before the Screening visit will be collected.

If a subject has previously tested positive for COVID-19 or has previously received a COVID-19 vaccine, it should be documented in the subject's medical history.

6.2 Efficacy Assessments

To minimize inter-observer variability, Investigators and evaluators/raters will be trained on each of the required assessments during an Investigator meeting, site initiation visit, and/or utilizing online assessments before enrolling subjects at their study site. Only trained evaluators/raters are permitted to perform the efficacy assessments. To the fullest extent possible, the same Investigator (or designated evaluator/rater) will perform all efficacy assessments for an individual subject throughout the study. If it is not possible for the same evaluator/rater to continue performing assessments, it is recommended that the primary and subsequent evaluator/rater both examine and discuss their respective scoring during at least 1 visit.

6.2.1 Assessments Completed by Investigator

6.2.1.1 Validated Investigator Global Assessment

The vIGA-AD™ of disease severity will be assessed at every clinic visit. The vIGA-AD™ is a global assessment of the current state of the disease. It is a 5-point morphological assessment of overall disease severity and will be determined according to the categories described in [Table 3](#) and [Appendix 3](#). To be eligible, subjects must have a vIGA-AD™ score of at least 3 or 4 at Screening and the Baseline visit (Day 1). Eli Lilly and Company (Lilly) developed the vIGA-AD™ scale for use in clinical trials. For more information on the vIGA-AD™ please refer to Appendix 3 and the website <http://www.eczemacouncil.org/research/investigator-global-assessment-scale/>

Table 3: Validated Investigator Global Assessment Scale for Atopic Dermatitis

Score	Category	Definition
0	Clear	No inflammatory signs of atopic dermatitis (no erythema, no induration/papulation, no lichenification, no oozing/crusting). Post-inflammatory hyperpigmentation and/or hypopigmentation may be present.
1	Almost clear	Barely perceptible erythema, barely perceptible induration/papulation, and/or minimal lichenification. No oozing or crusting.
2	Mild	Slight but definite erythema (pink), slight but definite induration/papulation, and/or slight but definite lichenification. No oozing or crusting.
3	Moderate	Clearly perceptible erythema (dull red), clearly perceptible induration/papulation, and/or clearly perceptible lichenification. Oozing and crusting may be present.
4	Severe	Marked erythema (deep or bright red), marked induration/papulation, and/or marked lichenification. Disease is widespread in extent. Oozing or crusting may be present.

6.2.1.2 Body Surface Area Affected

The assessment of the %BSA affected is an estimate of the percentage of total involved skin with AD. For the purpose of clinical estimation, the total palmar surface of the subject's palm and digits may be assumed to be approximately equivalent to 1% BSA. The %BSA affected by AD will be evaluated from 0% to approximately 100% [scalp excluded]). Details on calculation of approximate %BSA involvement in each subject are provided in [Appendix 4](#). Percentage BSA is a static assessment made without reference to previous scores.

6.2.2 Eczema Area and Severity Index

The EASI will be assessed at every clinic visit beginning with the Baseline visit. It quantifies the severity of a subject's AD based on both lesion severity and the %BSA affected ([Hanifin, 2001](#)). The EASI is a composite score ranging from 0 to 72 that takes into account the degree of erythema, edema/papulation, excoriation, and lichenification (each scored from 0 to 3 separately) for each of four body regions, with adjustment for % BSA involved for each body region relative to the whole body. A detailed procedure of EASI score calculation is provided in Appendix 4. The EASI score will be calculated in the CRF based on the subject's age, the rating scores for each region, and the number of handprints involved for each region.

6.2.3 Assessments Completed by Subject

[figure not shown]
6.2.3.1 Peak Pruritus Numeric Rating Scale

The PP NRS is a scale used to quickly assess itch/pruritus severity over a 24-hour period. The subject or caregiver will utilize the scale to assess peak pruritus QD and record the results in their daily diaries. The itch rating can be done before or after study drug administration since it should reflect the past 24 hours. On clinic visit days, the PP-NRS will be assessed in the clinic and not recorded in the diary. For subjects ages 2 to < 12 years, the PP-NRS will be completed by the parent or caregiver. For subjects ages \geq 12 years, the PP-NRS will be completed by the subject.

An example of the PP-NRS is provided below.

PP-NRS

On a scale of 0 to 10, with 0 being 'no itch' and 10 being 'worst itch imaginable', how would you rate your itch at the worst moment during the previous 24 hours?

PP-NRS © 2019 Regeneron Pharmaceuticals, Inc. and SAR&D. All rights reserved. Used with permission of Regeneron Pharmaceuticals, Inc. and SAR&D

6.3 Safety Assessments

6.3.1 Adverse Events

All AEs and SAEs will be collected from the time the subject signs the Informed Consent Form (ICF) until the final visit/contact with the subject. Additional safety information, including the definition of an AE and the methods for recording, evaluating, and assessing causality of AEs and the procedures for completing and transmitting SAE reports are provided in Section 8.

6.3.2 Brief Physical Examination

A brief physical examination will include, at a minimum, assessments of the skin, lungs, cardiovascular system, and abdomen (liver and spleen). Assess for changes in onset of menses (female participants) or sexual activity (male or female participants). Determine if there is a need for contraception or barrier use. Height and weight will be measured at Screening only. Investigators should pay special attention to clinical signs related to previous serious illness.

6.3.3 Vital Signs

Vital signs will be measured before blood collection for clinical laboratory assessments and PK analysis (where applicable) and will include measurements of systolic and diastolic blood pressure, pulse rate, and body temperature. Subjects should be in a seated position for at least 5 minutes before vital signs measurement.

6.3.4 Clinical Safety Laboratory Assessments

All protocol-required laboratory assessments must be conducted in accordance with the Study Reference Manual or Laboratory Manual and the protocol Schedule of Assessments ([Table 1](#)). Laboratory requisition forms must be completed, and samples must be clearly labeled with the subject number, protocol number, site number, and visit date. Details for the preparation and shipment of samples will be provided by the laboratory and are detailed in the Study Reference Manual or the Laboratory Manual. Reference ranges for all safety parameters will be provided to the site by the laboratory responsible for the assessments.

A list of clinical laboratory tests and parameters is provided in [Table 4](#).

All laboratory tests with values that are considered clinically significantly abnormal during participation in the study should be repeated until the values return to normal or baseline. If such values do not return to normal within a period judged reasonable by the Investigator, the etiology should be identified, if possible, and the Sponsor and Medical Monitor notified.

Table 4: Laboratory Tests

Diagnostic Screening Tests		

 • HBsAg • Hepatitis C antibody • Anti-HBc • Anti-HBs^a 		
 • Pregnancy tests: (serum at Screening and urine at other visits when performed; women of CBP only)^b • At the Investigator's discretion, subjects may be screened for alcohol and illicit drug use.
Serum Chemistry		

 • BUN • Creatinine • Glucose (fasting not required) • Sodium • Potassium • Chloride 	
 • Total carbon dioxide • Calcium • AST • ALT • Alkaline phosphatase 	
 • Uric acid • Total bilirubin (+fractionated if required) • Total protein • Albumin
Hematology		

 • Platelet count • RBC count • WBC count (absolute) • Reticulocyte count • Hemoglobin • Hematocrit 	
 • RBC Indices: • MCV • MCH • MCHC • Reticulocyte percentage 	
 • WBC Differential: • Neutrophils • Lymphocytes • Monocytes • Eosinophils • Basophils
Urinalysis		

 • Specific gravity • Microscopic examination (if blood or protein is abnormal) 		
 • Dipstick: pH, Glucose, Protein, Blood Ketones

a. Reflex test: a negative HBsAg and a positive anti-HBc may enroll if they have a positive anti-HBs demonstrating natural immunity

b. Pregnancy tests should be administered based on CBP, which may change after the start of the study (e.g. a premenarchal female subject experiences menarche or a female subject ceases to meet the criteria of CBP)

ALT = alanine aminotransferase; Anti-HBc = anti-hepatitis B core antigen; Anti-HBs = anti-hepatitis B surface antigen; AST = aspartate aminotransferase; BUN = blood urea nitrogen; CBP = child-bearing potential; HBsAg = hepatitis B surface antigen; MCH = mean corpuscular hemoglobin; MCHC = mean corpuscular hemoglobin concentration; MCV = mean corpuscular volume; RBC = red blood cell(s); WBC = white blood cell(s).

6.3.5 Investigator Assessed Local Tolerability Scale

At each specified study visit, the Investigator (or qualified evaluator) will assess the presence and overall degree of irritation at the application sites according to a 5-point LTS. The score will ideally represent an “average” across all application sites. To the fullest extent possible, the same Investigator (or designated evaluator) will perform all tolerability assessments for an individual subject throughout the study. If the subject is applying study drug to “sensitive areas”, a separate LTS will be used to assess the degree of irritation for each of these areas where study drug is being applied. The sensitive areas that will be assessed are face, neck, skin folds, axilla, inframammary, anal crux, and genitalia. An example of the LTS is shown in [Appendix 5](#). The LTS should be completed pre-dose at Baseline/Day 1, Day 8, and Day 28 when other

assessments are completed. Other than at the Baseline visit, the Investigator-assessed LTS should only be completed when the subject is currently receiving study drug (i.e. has applied at least one application in the last 48 hours).

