
 Incidence, frequency, and duration of treatment emergent adverse events (TEAEs) and serious adverse events (SAEs) Change from Baseline in laboratory values Change from baseline in vital signs Mean Investigator-assessed LTS scores by visit (overall and sensitive areas) Tapinarof plasma PK parameters on Day 1, if data permit, including: 
 area under the plasma concentration versus time curve from time zero to the last quantifiable concentration (AUC_{0-last}) maximum plasma concentration (C_{max}) time to maximum plasma concentration (t_{max}) time of last quantifiable concentration (t_{last}) Tapinarof plasma concentration on Day 28 	
Secondary:	

 Change in vIGA-AD™ score from Baseline at each study visit Proportion of subjects who have a vIGA-AD™ score of clear or almost clear (0 or 1) at each study visit Proportion of subjects with \geq50% improvement in EASI score from Baseline at each study visit Proportion of subjects with \geq75% improvement in EASI score from Baseline at each study visit Proportion of subjects with \geq90% improvement in EASI score from Baseline at each study visit Mean change and percent change in EASI score from Baseline at each study visit Mean change and percent change in %BSA affected from Baseline at each study visit Mean change and percent change in BSA x vIGA-AD™ values from Baseline at each study visit Proportion of subjects with a Baseline PP-NRS score \geq 4 who achieve \geq 4-point reduction in the PP NRS from Baseline at each study visit Proportion of subjects \geq 12 years old with a Baseline PP-NRS score \geq 4 who achieve a \geq 4-point reduction in PP-NRS score from Baseline at each study visit Proportion of subjects 2 to $<$ 12 years old with a Baseline PP-NRS score \geq 4 who achieve a \geq 4-point reduction in PP-NRS score from Baseline at each study visit Mean change in PP-NRS score from Baseline to Day 28 at each study visit by age group 	
Statistical Methods:	
Safety Analyses:	

 Analyses of the safety endpoints will be based upon the Safety population, which is defined as all enrolled subjects who receive at least 1 application of study drug. 	

- AEs will be summarized as incidence rates of any AEs, TEAEs, AEs of special interest, treatment-related TEAEs, TEAEs leading to study drug discontinuation, TEAEs leading to study discontinuation, and SAEs.

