- Changes in laboratory parameters and vital signs will be summarized using shift tables and descriptively for quantitative measures by visit.
- LTS scores will be summarized by visit.

Pharmacokinetics:

- Plasma concentration data will be listed and summarized by study visit. PK parameters will be presented in tabular and/or graphical format and summarized descriptively if data permit

Efficacy Analyses:

- Analyses of efficacy endpoints will be based upon the Safety population. Proportions will be summarized using frequency counts and percentages, and mean changes and percent changes will be summarized using descriptive statistics (mean, median, standard deviation, minimum and maximum).

Schedule of Assessments

Table 1: Schedule of Assessments

Procedures and Assessment	Screening	Treatment Phase					FU ^a	ET ^b
	V1	V2	V3	P/C	V4	V5	NA	
	Day -30 to Day -1	Baseline, Day 1	Day 8 (±1 day)	Day 15 (±2 days)	Day 28 (±2 days)	Day 35 (±3 days)	NA	
Informed consent	X							
Inclusion and exclusion criteria	X	X						
Demography	X							
Fitzpatrick skin type	X							
Brief physical exam ^c	X	X	X			X	X	X
Medical history ^d	X	X ^e						
Pregnancy test (females of child-bearing potential) ^f	X	X ^g				X		X
Blood sample for clinical laboratory assessments ^h	X					X	X ⁱ	X
Urinalysis	X					X	X ⁱ	X
Vital signs ^j	X	X	X			X	X	X
Study drug Dispensation / Collection ^k		D	C/D			C		C
Review instructions for study drug application ^l		X	X	X				
Dispense/collect subject diary of study drug application		D	C/D			C		C
Tapinarof cream administration in-clinic under site supervision ^m		X	X					
PK samples ⁿ	X	X				X		
AE/SAE review	X	X	X	X	X	X	X	X
Concomitant medication review	X	X	X	X	X	X	X	X
vIGA-AD TM score ^o	X	X	X			X	X	X
%BSA affected ^p	X	X	X			X	X	X
EASI ^p		X	X			X	X	X
LTS assessment by Investigator ^q		X	X			X		
PP-NRS (assessed pre-dose at visit, as applicable) ^r		X	X			X		
Enrollment (optional) in open-label long-term safety study						X		

- a. The Follow-up Visit will be performed for any subject who fails to qualify for participation in the open-label long-term safety study or qualifies to participate in the open-label long-term safety study but elects not to enroll in that study. A follow-up visit will be not completed for a subject who terminates early.
- b. Subjects who withdraw from the study before Day 28 (Visit 4) will complete an Early Termination Visit.

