7.7 Early Termination Visit

Subjects who withdraw early from the study will be asked to return to the study site to complete Early Termination assessments as follows:

- Brief physical examination
- Urine pregnancy test (females of child-bearing potential)
- Blood sample collection for clinical laboratory tests
- Urinalysis
- Vital signs measurement
- Collect study drug
- Collect study drug subject diary and PP-NRS diary and review for compliance
- AE recording
- Concomitant medication recording
- vIGA-AD™ score (excluding subject's scalp)
- %BSA affected calculation (excluding subject's scalp)
- EASI (excluding subject's scalp)

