7.8 Unscheduled Visit

Subjects may have an unscheduled visit for AE follow-up, study drug dispensation, make-up for a missed visit, or other reason. The following assessments may be performed as needed:

- Brief physical examination

- Urine pregnancy test (females of child-bearing potential)
- Blood sample collection for clinical laboratory tests (serum chemistry, hematology, diagnostic tests)
- Urinalysis
- Vital signs measurement
- Dispense and / or collect study drug
- Review instructions on how to apply study drug
- AE recording
- Concomitant medication recording
- Dispense and / or collect subject diaries
- vIGA-AD™ score (excluding subject's scalp)
- %BSA affected calculation (excluding subject's scalp)
- EASI (excluding subject's scalp)
- Assessment of itch (PP-NRS)
- Review subject diaries for treatment compliance

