13.3 Local Tolerability Scale (LTS) Scores

Local tolerability scale scores will be summarized with frequency counts and percent by visit (through Week 4/End of Treatment [EOT]). Additionally, observed values and change from baseline will be summarized by treatment and visit.

Local tolerability scale scores and change from Baseline scores at the sensitive areas (face, neck, skin folds, axilla, inframammary, anal crux, and genitalia) where study drug is applied will be summarized descriptively by visit and area for Investigator overall assessment, as well as listed by subject and anatomical site.

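### The local tolerability score, a primary endpoint, is not scheduled at Early Termination or unscheduled visits and depends on recent dosing, so children who stop for irritation leave the later visit means

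*Protocol*

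**What the plan says.** The Synopsis lists "Mean Investigator-assessed LTS scores by visit (overall and sensitive areas" among the primary endpoints, and Protocol Section 2 repeats it.

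Protocol 6.3.5 fixes the times: "The LTS should be completed pre-dose at Baseline/Day 1, Day 8, and Day 28". It adds that, other than at Baseline, the scale "should only be completed when the subject is currently receiving study drug", explained as a subject who "has applied at least one application in the last 48 hours".

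In Table 1 the row "LTS assessment by Investigator" carries three marks, which fit those three visits. None is left for Follow-up or Early Termination.

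Section 7.7 opens with "Subjects who withdraw early from the study will be asked to return to the study site to complete Early Termination assessments as follows". The list that follows includes vIGA-AD, %BSA and EASI but not the LTS. Section 7.8 ("The following assessments may be performed as needed") lists those three plus the itch score, again without the LTS.

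Protocol 10.6 and SAP 10.4 rule out imputation for this endpoint, and Protocol 10.6 restricts summaries to observed data. SAP 13.3 states: "Local tolerability scale scores will be summarized with frequency counts and percent by visit", through Week 4/End of Treatment, with observed values and change from baseline. It has no worst-score row and no count of unscored children.

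**The concern.** The rule that decides whether a score exists is linked to the thing being scored. The protocol's own provisions send children with troublesome irritation to the visits where the LTS is not scheduled:

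- Section 4.6.1 withdraws a child with a drug-related Grade 3 or 4 adverse event and requires an Early Termination visit.
- Section 8.1.3 asks that a child reporting significant irritation between visits be seen at an unscheduled visit if possible.
- Section 8.1.3 also allows drug to be stopped and restarted for contact dermatitis. A gap of more than 48 hours over Day 8 or Day 28 removes that visit's score.

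Appendix 5 describes a score of 2 as not needing a treatment change and says nothing similar for 3 or 4. The upper end of the scale is therefore the part most likely to go with stopping, and so to be lost. At stake is whether a primary tolerability table, shown by age cohorts of about 12, represents all treated children or mainly those who tolerated the cream well enough to continue.

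**Working it through.** The plan has no figure to reproduce. Protocol 10.2 states no hypothesis and bases the sample size mainly on feasibility. No dropout rate, LTS mean or LTS spread is given.

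**Step 1. Who loses which score** (Protocol 6.3.5, 7.7, 7.8)

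- Withdraws before Day 8: no post-baseline LTS is scheduled.
- Stops for good after Day 8, more than 48 hours before Day 28: Baseline and Week 1 are kept, Week 4 is lost.
- Interrupts for more than 48 hours over Day 8 or Day 28: that visit is lost.
- Last application within 48 hours of Day 8 or Day 28, and attends: scored as planned.

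**Step 2. What the SAP does with the gap.** Under SAP Section 6, percentages exclude the missing category, so an unscored child leaves the denominator. SAP Section 7 would assign Early Termination and unscheduled values to Week 1 or Week 4, but no LTS is scheduled there to assign.

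**Step 3. Size.** Let N be the children who would be scored at a visit, d the number unscored, s their true score and m the observed mean.

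Full mean = ((N − d) × m + d × s) / N, so understatement = (d/N) × (s − m).

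N is 36 overall and about 12, minimum 10, per cohort (SAP Section 5). The values of m, s and d are assumptions. With d = 1 and s = 3:

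| N | m (reported) | Full mean | Understatement |
|---|---|---|---|
| 36 | 0.20 | (35 × 0.2 + 3)/36 = 0.28 | 0.08 |
| 36 | 0.50 | (35 × 0.5 + 3)/36 = 0.57 | 0.07 |
| 12 | 0.20 | (11 × 0.2 + 3)/12 = 0.43 | 0.23 |
| 12 | 0.50 | (11 × 0.5 + 3)/12 = 0.71 | 0.21 |
| 10 | 0.20 | (9 × 0.2 + 3)/10 = 0.48 | 0.28 |
| 10 | 0.50 | (9 × 0.5 + 3)/10 = 0.75 | 0.25 |

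Over s = 2 to 4 and m = 0.2 to 0.5, one unscored child understates the mean by 0.04 to 0.11 (N = 36), 0.13 to 0.32 (N = 12) or 0.15 to 0.38 (N = 10). Two unscored children give 0.08 to 0.21 (N = 36) or 0.25 to 0.63 (N = 12).

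If one unscored child is the only one at LTS 3 or above, the reported share is 0% instead of 1/36 = 2.8%, 1/12 = 8.3% or 1/10 = 10%.

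**Step 4. How likely is at least one such child?** P = 1 − (1 − p)^N, where p is an assumed chance that a child stops or interrupts for irritation. For p = 2%, 5% and 10%, P is 52%, 84% and 98% among 36, and 22%, 46% and 72% among 12.

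**Step 5. Would collection alone repair the table?** Not fully. In SAP Section 7 the Week 1 window runs to Day 18, and the value closest to Day 8 is used. An Early Termination score on Day 16 (8 days from target) would lose to a scheduled score on Day 8 (0 days), so it would reach no visit summary. From Day 19, an Early Termination score falls in the Week 4 window however long the child has been off drug, unless the window has ended.

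**The case against.** The best defence is that the 48-hour condition is deliberate: the LTS is meant to describe irritation in a child who is using the cream. A score taken days after stopping partly measures recovery. If such scores entered the Week 1 or Week 4 mean through the SAP windows, they too could flatter tolerability. This stands and shapes the fix. It does not explain why the LTS is missing from Early Termination and unscheduled visits that fall within 48 hours of an application.

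The second defence is that the signal is captured elsewhere. Contact dermatitis is an adverse event of special interest with detailed collection (Protocol 8.1.3) and extended summaries (SAP 13.2). Events leading to discontinuation are tabulated, the Early Termination physical examination covers the skin, and the number of observations is reported. This also stands for the study as a whole, but the LTS table does not say why children are unscored.

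Third, the consequence is bounded: the LTS is one of several primary endpoints, all descriptive, with no hypothesis or decision rule resting on it. Video scoring under Section 6.6 covers regularly scheduled visits and does not add the LTS to Early Termination.

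A reader might infer more than the documents support:

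- That a child who stops is never scored. A child who stops after Day 8 can keep the Week 1 score, and one dosed within 48 hours of a scheduled visit is still scored there.
- That the plan conceals irritation. The adverse event and disposition tables show these children.
- That the mean is known to be biased. Children may leave for unrelated reasons, and no rates are given.
- That each omitted child at score 3 costs a cohort of 12 a fixed 3/12 = 0.25. That requires every other child to score 0, which is unlikely on a scale that scores erythema in children with at least moderate disease.

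**Conclusion.** The gap is real and consistent across Table 1 and Sections 6.3.5, 7.7 and 7.8. Children who stop or interrupt for irritation can lose their later LTS scores, and those who stop before Day 8 may contribute none after Baseline. The likely effect is an LTS mean and severe-score count that look too favourable. That direction holds whenever the unscored children would have scored above the observed mean, which is plausible but not shown.

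With one unscored child at LTS 3 and an observed mean of 0.2, the understatement is about 0.08 points overall and 0.23 in a cohort of 12. It therefore matters mainly for the age-cohort tables. These sizes rest on assumed scores and counts. The problem is confined to the LTS endpoint, and the study's other safety summaries remain informative.

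**What to change.** Protocol: add the LTS to the Early Termination column of Table 1 and to the lists in Sections 7.7 and 7.8. Let it be scored at those visits whatever the time since last application, and record that time.

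SAP 13.3:

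- Keep scores taken more than 48 hours after the last application out of the Week 1 and Week 4 means, and present them separately. State that this overrides the Section 7 windows.
- Add a worst post-baseline LTS row per child that includes Early Termination and unscheduled scores. SAP 13.2 already takes the most extreme level for events of special interest.
- Report the number of children unscored at each visit, with reasons.

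If collection can no longer change, the count of unscored children with reasons, cross-referenced to events leading to discontinuation, can still be added in the SAP alone.

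The cost is one 5-point score at visits where the skin is or can be examined, plus amendment and SAP wording. Some off-drug scores will partly reflect recovery; the separate presentation makes that visible. No treatment rule changes.
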